5.9.2 Primary Efficacy Endpoint

The primary efficacy endpoint is the proportion of clinical responders at week 12. The clinical response is a composite measurement of MCS and the rectal bleeding score. It is defined as:

a) ≥ 3-point reduction in MCS, a 30% or greater decrease from the baseline score,

AND

b) 1-point or greater decrease of the rectal bleeding subscale or an absolute rectal bleeding score of 0 or 1 at Week 12.

The proportion of response rate will be summarized with frequencies and percentages along with 2-sided 95% exact Clopper-Pearson confidence interval at Week 12.

5.9.3 Secondary Efficacy Endpoints

The secondary endpoints (1, 2, 3, 5, 6, 8, 10) of clinical outcomes listed in Section 3.2.1 will be summarized with frequencies and percentages along with 2-sided 95% exact Clopper-Pearson confidence interval at given weeks.

The changes from baseline of secondary endpoints (4,7,9) including total score of IBDQ at Weeks 12 and 26 will be analysed separately using Analysis of Covariance model (ANCOVA) with baseline value as covariate. The descriptive statistics and the absolute change from baseline will be presented for each time point. Least square means and 95% confidence interval (CI) will also be provided at each assessment time point.

The estimated proportion of primary and secondary end points and 95% CI at each week will be displayed graphically using line graph. A line plots showing the mean change and 95% CI from baseline vs. time in weeks for secondary endpoints will be produced for mITT population.

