7. STATISTICAL CONSIDERATIONS

This is a phase II, open labelled, multiple dose study to be held at multiple study centers. The trial was designed to assess the efficacy and safety of Neihulizumab treatment in moderate-severe ulcerative colitis patients. Due to the small number of patients expected to be enrolled at each center, all summaries and analyses will be performed using data pooled across centers. Unless otherwise specified, continuous variables will be summarized with the number of non-missing observations, mean, standard deviation, median, maximum and minimum displayed. Categorical data will be summarized as counts and percentages. Missing data will not be estimated or carried forward in any of the analyses.

Patient data will be listed, sorted by investigative center and patient number. Deviations from the statistical analysis plan will be documented in the clinical trial report.

Except where other software may be deemed more appropriate (e.g., S-Plus or R), all analyses will be performed using SAS Version 9.2 statistical software (SAS Institute, Cary, NC). Details of the statistical analysis (beyond those specified below) will be defined in the TSAP.

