4 INVESTIGATIONAL PLAN

4.1 Overall Study Design and Plan

This is a single arm, open label, multiple dose, multi-center study to be conducted in 12-18 centers in United States (US) in 30-40 patients with a diagnosis of moderate to severe active ulcerative colitis, refractory or intolerant to anti-TNF α and/or anti-integrin treatments. Due to the COVID-19 pandemic, the holding of patient enrollment, as well as slow patient enrollment prior to the pandemic, the study has been closed out and the data will be analyzed at this time. Therefore, only available data from the patients will be included in the analysis.

Per protocol amendment 4, a total of 10 doses of Neihulizumab at 9 mg/kg will be administered to patients over 12 weeks on Day 1 (Week 0), Day 8 (Week 1), Day 15 (Week 2), Day 22 (Week 3), Day 29 (Week 4), Day 36 (Week 5), Day 43 (Week 6), Day 50 (Week 7), Day 64 (Week 9), and Day 78 (Week 11).

Whereas the patients enrolled under Protocol amendments 1-3, a total of 8 doses of Neihulizumab at 9 mg/kg are administered on Day 1 (Week 0), Day 8 (Week 1), Day 15 (Week 2), Day 22 (Week 3), Day 29 (Week 4), Day 43 (Week 6), Day 57 (Week 8), and Day 71 (Week 10).

Patients will be followed up on Day 84 (Week 12, End of Treatment, primary endpoint), Day 112 (Week 16), Day 140 (Week 20) and Day 182 (Week 26, End of Study) after the first dose of Neihulizumab.

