5.2 General Presentation Considerations

Due to the small number of patients expected to be enrolled at each center, all summaries and analyses will be performed using pooled patients across centers.

Unless otherwise specified, continuous data will be summarized with the number of non-missing observations, in terms of the mean, standard deviation (SD), median, minimum, maximum and number of observations, unless otherwise stated. Continuous data that are expected to be skewed will be presented in terms of the maximum, upper quartile, median, lower quartile, minimum and number of observations. The minimum and maximum will be reported to the same number of decimal places as the raw data recorded in the database. The mean, median, lower quartile and upper quartile will be reported to one more decimal place than the raw data recorded in the database. The SD will be reported to two more decimal places than the raw data recorded in the database. In general, the maximum number of decimal places reported shall be four for any summary statistic.

Categorical data will be summarized in terms of the number of patients providing data at the relevant time point (n), frequency counts and percentages.

Percentages will be presented to one decimal place. Percentages will not be presented for zero counts.

Confidence intervals will be presented to one more decimal place than the raw data.

The patients enrolled under Protocol amendments 1-3 were administered 8 doses of study medication over 11 weeks whereas the patients enrolled under amendment 4 will be administered

10 doses over 12 weeks. Therefore, the statistical analyses and summary tables will be performed by following groups: Group 1: the patients enrolled under amendments 1 to 3, Group 2: the patients enrolled under amendment 4.

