5.9 Efficacy Evaluation

5.9.1 Analysis and Data Conventions

5.9.1.1 Handling missing data for Efficacy

All missing values will be treated as a non-responder for primary and secondary binary endpoints. A supportive analysis will be performed using only observed data for the primary and secondary binary endpoints. The primary imputation method for any missing data for continuous variable for secondary efficacy endpoints will be the last observation carried forward (LOCF) approach.

If percentage of missing values at Week 12 and 26 is above 10% overall, then multiple imputation analysis will be performed.

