5.11.2 Quality of Life

To examine the quality of life in the patient population, a self-administered IBD questionnaire containing 32 questions identifiable to four dimensions: systemic symptoms (S), bowel symptoms (B), social Function (SF), and emotional function (E) will be used. The score of the questionnaire will be used to determine subjective health status for patients with inflammatory bowel disease over time.

IBDQ four dimensions:

- Bowel symptoms (B) – Question #s: 1, 5, 9, 13, 17, 20, 22, 24, 26, and 29
- Emotional function(E) – Question #s: 3, 7, 11, 15, 19, 21, 23, 25, 27, 30, 31, 32
- Systemic symptoms (S) – Question #s: 2, 6, 10, 14, 18
- Social function (SF) –Question #s: 4, 8, 12, 16, and 28.

The scoring of each question is in 1-7 scale. The higher the score the less quality of life is impaired. The IBDQ is calculated by summing the score of each question resulting in a maximum 224 and minimum of 32. If >50% of the questions are left unanswered the total will be treated as missing. The IBDQ questions with above 4 dimensions will be given in the Appendix 1.

Total IBDQ and the change of it from baseline will be summarized by each visit (Baseline, Week 12, and EOS/Week 26) using descriptive statistics. The number and proportion of patients with total IBDQ increased at least 16 points from baseline will also be summarized. Improvement or deterioration of each dimension from baseline to EOT will be compared using paired t-test. By subject listings of these data should be provided.

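### The single-arm ANCOVA intervals for change in endpoints 4, 7 and 9 hold only conditional on the observed baselines and can be too narrow for the population mean change; separately, the protocol and SAP missing-data rules conflict, for the primary endpoint as well

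*SAP*

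**What the plan says.** **Interval.** SAP 4.1: "This is a single arm, open label, multiple dose, multi-center study". SAP 5.2 states that "the statistical analyses and summary tables will be performed by following groups", the groups being patients enrolled under Amendments 1-3 and under Amendment 4. Under SAP 5.9.3, changes in endpoints 4, 7 and 9 "will be analysed separately using Analysis of Covariance model (ANCOVA) with baseline value as covariate"; no other model term is named. It continues: "Least square means and 95% confidence interval (CI) will also be provided at each assessment time point". The same section plans descriptive statistics of change and a plot: "A line plots showing the mean change and 95% CI from baseline vs. time in weeks". For the four IBDQ dimensions, SAP 5.11.2 says: "Improvement or deterioration of each dimension from baseline to EOT will be compared using paired t-test".

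**Missing data.** Protocol section 7: "Missing data will not be estimated or carried forward in any of the analyses". The same section leaves to the SAP only details beyond those the protocol specifies. SAP 5.9.1.1 counts missing values as non-response for primary and secondary binary endpoints, with an observed-data supportive analysis. It says the primary imputation method for any missing "continuous variable for secondary efficacy endpoints will be the last observation carried forward (LOCF) approach". It adds multiple imputation if more than 10% of values are missing overall at Weeks 12 and 26, naming no endpoint.

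**The concern.** ANCOVA is useful when arms are compared, because it removes chance baseline imbalance from the contrast. Here there is no contrast. Within one group the covariate leaves the estimate where it was and takes baseline-explained variance out of the standard error. In an uncontrolled trial, readers will take the interval as the uncertainty of the average change in patients like these. It answers a narrower question, namely the mean change given the baselines that happened to be enrolled, and the SAP does not say which is intended. The IBDQ dimensions get a paired t-test, whose standard error does include baseline variation, so the total and the parts of one questionnaire would be treated differently.

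On missing data, the two documents cannot both be followed. Until they are reconciled, results can be computed in more than one way.

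**Working it through.** **The plan's own figure.** The documents give no SD, correlation, interval width or power for endpoints 4, 7 and 9. Their only power statement concerns the primary response rate and does not bear on this point. Every SD, correlation and group size below is therefore an assumption. The SAP plans 30-40 patients in total, split into two groups, and reports early closure without giving the number enrolled.

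**Step 1: formulas.** Let D be change, X baseline, q = corr(X, D), and n the group size.
- LS mean at the mean baseline = mean of D.
- ANCOVA half-width: t(n-2) × SD(D) × sqrt(1 - q²) / sqrt(n).
- One-sample t half-width: t(n-1) × SD(D) / sqrt(n).
- The large-sample width ratio is sqrt(1 - q²), and coverage of the population mean change is 2Φ(1.96 × sqrt(1 - q²)) - 1. For |q| = 0.3, 0.5, 0.6 this gives 93.8%, 91.0%, 88.3%. A larger n does not cure it.

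**Step 2: small samples.** Simulation with normal data; the target is the population mean change.

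| n | \|q\| | ANCOVA coverage | width relative to t interval |
|---|---|---|---|
| 10 | 0.3 / 0.5 / 0.6 | 94.1 / 92.0 / 89.6% | 0.97 / 0.88 / 0.81 |
| 20 | 0.3 / 0.5 / 0.6 | 94.0 / 91.4 / 89.0% | 0.96 / 0.87 / 0.80 |
| 40 | 0.3 / 0.5 / 0.6 | 93.8 / 91.0 / 88.5% | 0.96 / 0.87 / 0.80 |

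The one-sample t interval covers about 95% throughout. So does the ANCOVA interval when the target is the mean change conditional on the observed baselines.

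In very small groups the lost degree of freedom dominates. At n = 5 the ANCOVA interval is on average 1.10 and 1.07 times as wide for |q| = 0.2 and 0.3; at n = 6, about 1.05 and 1.02 times. Coverage there is still marginally low, at 94.3-94.7%.

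**Step 3: IBDQ-like scale.** Assume SD 30 at both times and baseline-to-follow-up correlation r. Then SD(D) = 30 × sqrt(2(1 - r)) and |q| = sqrt((1 - r)/2). At n = 20:
- r = 0.3: SD(D) = 35.5, |q| = 0.59; half-width 13.4 points by ANCOVA against 16.6 by t.
- r = 0.5: SD(D) = 30.0, |q| = 0.50; 12.2 against 14.0.
- r = 0.7: SD(D) = 23.2, |q| = 0.39; 10.1 against 10.9.

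Coverage is 89 / 91 / 93%. With SD 30 at baseline and 35 at follow-up it is 92 / 93 / 95%.

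**Step 4: endoscopic subscore.** Entry requires a subscore of at least 2, so baseline is 2 or 3 (SD about 0.5). With follow-up SD 0.7-0.9 and n = 20, the ANCOVA interval is 3-8% narrower at r = 0.3 and 0-3% at r = 0.5, with coverage 93-95%. Endpoint 7 has no scenario of its own; the general table applies.

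**Step 5: missing data.** Both schedules place endpoints 4, 7 and 9 only at screening, Week 12 and Week 26. A patient with no Week 12 value and no early-termination assessment has only baseline to carry, so change = 0. With missing share m, the mean becomes (1 - m) × observed gain. For an assumed observed IBDQ gain of 10 to 25 points:
- m = 10%: a fall of 1.0 to 2.5 points.
- m = 20%: a fall of 2.0 to 5.0 points.

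**The case against.** **Conditional inference is legitimate.** This stands: the interval is a correct conditional one, so a reader who infers that it is simply invalid goes too far. No test or success rule depends on it, and n, mean and SD of change are planned, so the t interval can be recovered from the tables. What remains is that the reported interval has no stated target and will be read as the wider one.

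**The group structure is not fixed.** Also fair. SAP 5.2 does not say whether the ANCOVA is fitted separately by group. If amendment group were a factor in one model, LS means would be taken at a common baseline and would differ from the raw group means. Their standard errors would still be conditional on baseline.

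**The size is assumed.** True. Coverage near 89% needs |q| of about 0.6, and the narrowing disappears or reverses in groups of 5-6 with |q| up to 0.3.

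**The IBDQ contrast and the plot.** SAP 5.11.2 plans a test for the dimensions rather than an interval, so that inconsistency is modest. The plot wording most naturally means the raw mean with its own interval, and needs only a sentence to confirm it.

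**LOCF does not always carry baseline.** Correct. Footnote 1 of the schedules asks for end-of-study assessments at the last visit when a patient cannot continue, and SAP 5.5.2 slots early-termination assessments into visit windows. A reader might infer that LOCF is the wrong method; the documents do not establish that it is more biased than the alternatives. Whether multiple imputation replaces LOCF is only missing detail: LOCF is called primary, so multiple imputation most naturally supplements it.

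**Conclusion.** Both parts hold, at minor to moderate weight.

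(a) Fitted separately by group, the LS-mean interval is valid given the observed baselines but under-covers the population mean change when baseline and change are correlated. Under the assumed range (|q| 0.3 to 0.6, n = 10 to 40) coverage runs from about 94% down to 89%. The practical case is the IBDQ total; for the endoscopic subscore the effect is small. This part touches secondary endpoints only.

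(b) The conflict between protocol section 7 and SAP 5.9.1.1 is direct. A reader might infer that the primary endpoint is untouched, since LOCF is confined to continuous secondary endpoints. The documents do not support that: the protocol's bar covers every analysis, non-responder imputation applies to the primary endpoint, and the multiple-imputation sentence names no endpoint while Week 12 is the primary time point. The 2-5 point shift at 20% missing rests on an assumed gain and on baseline being carried. It shows that the choice of rule matters, not which rule is right.

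**What to change.** **SAP 5.9.3.** Make the mean change from baseline at Weeks 12 and 26 within each amendment group, with a one-sample (paired) t 95% interval, the main result, and state that the mean-change plots use it. If the ANCOVA would have been fitted separately by group, this step leaves point estimates unchanged; if group were a factor in one model, they would become the raw group means. In groups of 10 or more, intervals generally widen when baseline and change are correlated (at n = 20 and SD 30/30, from 13.4 to 16.6 IBDQ points at r = 0.3, and from 10.1 to 10.9 at r = 0.7). In groups of 5-6 with a weak correlation they may narrow slightly.

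**Protocol section 7 and SAP 5.9.1.1.** Reconcile them into one rule covering the primary, other binary and continuous endpoints. Name the endpoints that multiple imputation covers and its role beside LOCF, and say whether a baseline value may be carried forward. Show observed-case results with n for the continuous endpoints, as the SAP already does for the binary ones. Settling this rule can itself move estimates.

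**Cost.** Wording and simpler programming for the interval, one reconciled paragraph on missing data and one extra set of observed-case tables. No new data are needed.

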5.9.4 Exploratory Efficacy Variables

The change of biomarkers of faecal calprotectin and c-reactive protein (CRP) at Week 4, 9, 12, 16, 20, and 26 will be summarized using descriptive statistics. The association between biomarkers and Cmax and the primary efficacy endpoint of UC will be examined.

5.10 Safety Evaluation

All safety summaries and analyses will be based upon the Safety Set as defined in Section 4.5.

5.10.1 Extent of Exposure

A by-patient listing of the duration of exposure (total number of days and total dose (mg) will be provided

5.10.2 Adverse Events

All TEAE summaries will include the frequency count of patients with TEAE and the percentage. Patients with multiple TEAEs will be counted only once for each TEAE category.

An overall summary of TEAE will include number of patients in the following TEAE categories:

- Any TEAE
- Any TEAE with Grade ≥ 3
- Any treatment related TEAE by study medication
- Any treatment related TEAE with Grade ≥ 3 by study medication
- Any TEAE leading to treatment discontinuation
- Any TEAE leading to dose reduction or interruption
- Any serious AE
- Any treatment related serious AE by study medication
- Any AE with outcome of death

TEAE will also be summarized by MedDRA system organ class (SOC) and preferred term (PT) for the following TEAE categories:

- Any TEAE
- TEAEs with Grade ≥ 3
- Treatment related TEAE
- Any TEAE leading to discontinuation
- Any TEAE leading to dose reduction or interruption
- Any serious AE

All death and SAEs will be listed.

5.10.3 Adverse Events of Special Interests

Potential significant risks due to infusion toxicities and infection related to immunosuppression of Neihulizumab will be summarized by SOC and PT. A by-patient listings will also be provided.

5.10.4 Clinical Laboratory Evaluation

Laboratory results will be summarized using standard international (SI) units, as appropriate. For all quantitative parameters listed in 3.2.2.2, the actual value and the change from baseline to each post-baseline visit and to the EOT will be summarized by visit using descriptive statistics. Qualitative parameters listed in 3.2.2.2 will be summarized using frequencies (number and percentage of patients), and changes from baseline to each post-baseline visit and to the EOT will be reported using shift tables. Percentages will be based on the number of patients with both non-missing baseline and relevant post-baseline results.

Laboratory test results will be assigned a low/normal/high (LNH) classification according to whether the values are below (L), within (N), or above (H) the laboratory parameter's reference range. Similar shift tables will be used to compare the baseline LNH classification to the LNH classification for the highest and lowest value during the treatment period.

A by-patient listing of laboratory will be provided with abnormal values flagged.

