2.3 BENEFIT - RISK ASSESSMENT

With this novel mechanism of action Neihulizumab is anticipated to be effective in treating T-cell mediated autoimmune diseases. In both Studies 2012.005.01 and 2014.002.01, signs of efficacy were clearly observed for psoriasis. Study 2014.009.01 also demonstrated clinical efficacy for psoriatic arthritis (see [Section clinical studies](#)). Patients of UC might benefit from the trial because T cells play a pivotal role in the pathogenesis of UC, and based on Neihulizumab's novel mechanism of action it is expected that patients with UC are going to benefit from the treatment of Neihulizumab.

Risk of hematopoietic cell depletion

In Study 1304.1, Study 2012.005.01, Study 2014.002.01 and Study 2014.009.1, Neihulizumab single or multiple doses were well tolerated. No cytokine release syndrome or hematopoietic cell depletion was observed in these four studies. A mild, clinically insignificant, transient, and reversible decrease in the mean and median total leukocyte counts was observed in the 3 mg/kg group in trial 2012.005.01 and in the 6 mg/kg and 9 mg/kg groups in trial 2014.002.01, and in study 2014.009.01 where 7 doses of Neihulizumab at 9 mg/kg were administered. Although the risk that Neihulizumab will affect stem cells is convincingly low, it is still critical that careful long-term monitoring of peripheral blood cells is carried out to rule out a clinically significant adverse effect of Neihulizumab on bone marrow stem cells *in vivo*.

Risk of impaired immune function

Neihulizumab has been demonstrated to induce apoptosis selectively in late stage activated T-cells. This selectivity suggests that naïve and resting memory T-cells would be spared from deletion by Neihulizumab, and therefore that Neihulizumab may be less immunosuppressive than pan-T-cell depleting mAbs or the systemic immunomodulating agent such as cyclosporine. However, it cannot be ruled out that depletion of activated T-cells by Neihulizumab may lead to a transiently increased risk of infection. This risk will be addressed by clinical monitoring for adverse events during the treatment and observation periods.

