3.3.3 Exclusion Criteria

GI related exclusion criteria:

1. Indeterminate colitis (IBD-U) or suspected Crohn's disease;
2. Any history of colectomy;
3. Presence of an ileostomy or colostomy;
4. A history or evidence of colonic mucosal dysplasia;
5. Short gut syndrome.

General health related exclusion criteria:

6. Pregnant or lactating;
7. Inability to comply with study protocol in the opinion of the investigator;
8. History of dysplasia or malignancy in recent 5 years, except completely excised basal cell carcinoma or squamous cell carcinoma of the skin or carcinoma in situ of the cervix;
9. Cirrhosis or active alcohol abuse per the judgement of investigator;
10. Poorly controlled diabetes (HbA1c $> 8.0\%$);
11. Significant screening ECG abnormalities, including evidence of acute myocardial infarction, complete left bundle branch block, second-degree heart block, or complete heart block;
12. Impaired renal function (calculated creatinine clearance < 60 mL/min);
13. Impaired hepatic function in the absence of diagnosis of primary sclerosing cholangitis serum transaminase $> 2.5x$ ULN, alkaline phosphatase $> 2.5x$ ULN, or increased total bilirubin judged by the investigator to be clinically significant, or a diagnosis of primary

sclerosing cholangitis, serum transaminases > 3x ULN, alkaline phosphatase > 3x ULN, or total bilirubin > 2.5x ULN judged by the investigator to be clinically significant;

14. Moderate to severe anemia (Hb < 8g/dL);
15. Thrombocytopenia (platelet count < 75,000/uL);
16. Evidence of current or previous clinically significant disease, medical condition or finding in the medical examination that in the opinion of the investigator, would compromise the safety of the patient or quality of the data;
17. Requiring parenteral corticosteroid treatment.
18. Received any investigational product within 1 year
19. History of drug abuse according to the Diagnostic and Statistical Manual of Mental Disorders, 5th edition (DSM-V) criteria within 12 months prior to screening or positive drug screening tests.

Infection related exclusion criteria:

20. Human immune deficiency virus (HIV) infection or known HIV-related malignancy;
21. Acute or chronic hepatitis B or C, or carrier status. Patients with anti-HBc Ab but with undetectable anti-HBs Ab should also be excluded;
22. Positive IgM antibody titers in the presence of negative IgG titers to Epstein-Barr virus;

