23. Positive stool test for ova or parasites, positive stool culture for pathogens, or positive stool toxin assay for *Clostridium difficile* at screening. Patients with the positive stool toxin assay for *C. difficile* at screening could be rescreened if they are being treated for *C. difficile* and a repeat stool toxin assay at least 4 weeks after the completion of treatment is negative with no evidence of recurrence;
24. Intestinal mucosa biopsy positive for cytomegalovirus (CMV) at screening;
25. Positive screening test for latent *Mycobacterium tuberculosis* (TB) infection. Patients with a history of latent TB infection who received an appropriate and documented course of therapy can be included if the screening examination and a chest x-ray performed ≤ 3 months before screening revealed no evidence of current active infection. If a Quantiferon TB test is indeterminate, the test should be repeated, and if the result is again indeterminate, such patient should be excluded;
26. History of any opportunistic infection ≤ 12 weeks before D1 dosing;
27. Any current or recent (≤ 4 weeks before D1 dosing) symptoms/signs of infection;

28. Received oral antibiotics \leq 4 weeks before D1 dosing or intravenous antibiotics \leq 8 weeks before D1 dosing;
29. Received a live attenuated vaccine \leq 4 weeks before D1 dosing;
30. Neutropenia (absolute neutrophil count $<$ 1,500/uL);
31. Lymphocytopenia (absolute lymphocyte count $<$ 500 /uL);

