7.1.2 Safety analyses

Safety analyses will be performed based on the mITT set. No hypothesis testing is planned prospectively.

Adverse events will be coded using the Medical Dictionary for Drug Regulatory Affairs (MedDRA). Adverse events occurring prior to drug administration will be assigned to the screening period. All other adverse events will be assigned to the treatment periods for evaluation.

Independent of this rule, the relationship of an adverse event to the study drug treatment will be assessed by the investigator. The evaluation of adverse events will comprise various frequency tabulations.

Descriptive statistics of demographic data, of time-courses and of changes from baseline of vital signs and physical examination will be provided.

Descriptive statistics of laboratory values over time and for the difference from baseline will be provided. Frequency tables of changes with respect to the reference range between baseline and last value on treatment will also be presented.

Relevant findings in ECG measurements will be reported under “Relevant Medical History /Baseline Conditions” (at screening).

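### The laboratory shift tables use only low, normal and high classes, so no planned table counts patients by how severely their blood counts or other laboratory values worsen

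*SAP*

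**What the plan says.** SAP 5.10.4 classes each laboratory result by whether "values are below (L), within (N), or above (H) the laboratory parameter's reference range". Its shift tables then "compare the baseline LNH classification to the LNH classification for the highest and lowest value during the treatment period".

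Protocol 7.1.2 also plans a reference-range table, based on a different on-treatment value: "Frequency tables of changes with respect to the reference range between baseline and last value on treatment will also be presented".

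The entry floors are in Protocol 3.3.3. Exclusion 14 reads "Moderate to severe anemia (Hb < 8g/dL"), exclusion 15 reads "Thrombocytopenia (platelet count < 75,000/uL"), and exclusion 31 removes patients with lymphocytes below 500/uL. Exclusion 30 sets the neutrophil floor at 1,500/uL. The list gives no floor for total leukocytes.

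Protocol 2.3 records falls in mean and median total leukocytes in earlier studies, described as mild, reversible and without clinical significance. On possible effects on bone marrow stem cells it adds that "it is still critical that careful long-term monitoring of peripheral blood cells is carried out".

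Three other planned outputs bear on the point:
- SAP 5.10.4 summarises actual values and changes from baseline by visit, and SAP 5.2 includes the minimum and maximum among the descriptive statistics.
- SAP 5.10.4 plans a listing by patient in which abnormal results are marked.
- SAP 4.2.2.1 grades adverse events by CTCAE v4.03, and SAP 5.10.2 tabulates treatment-emergent events of grade 3 or higher.

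**The concern.** A three-class shift table has one class below the reference range. A patient who starts there has no lower class to move to, so further worsening leaves the cell unchanged. A patient who starts in the normal class moves to low whether the fall is slight or deep. The table therefore records that a value is low, but not how low.

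This matters because laboratory change is a named safety endpoint (Protocol 5.2.1) and the protocol gives blood counts particular weight. The trial is open-label and single-arm, and SAP 5.13 plans no data monitoring committee. A count of severe laboratory falls that does not rest on case-by-case judgement would be useful, and none is planned.

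**Working it through.** The plan states no figure on this point, so there is nothing to reproduce. The check applies the SAP's own classification rule to patients whom the entry criteria admit.

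**Inputs.** The floors come from Protocol 3.3.3. The documents give no reference ranges, so the lower limits of normal (LLN) are assumptions, tried over a range.

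**Rule.** Class = L if value < LLN, otherwise N (the upper limit is not in play here).

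**Step 1: is a patient at the entry floor already low?** Ratio = floor / LLN. Below 1 means L at baseline.

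| Analyte | Floor | Assumed LLN | Ratio |
|---|---|---|---|
| Haemoglobin (g/dL) | 8 | 11, 12, 13, 13.5 | 0.73, 0.67, 0.62, 0.59 |
| Platelets (/uL) | 75,000 | 130,000, 140,000, 150,000 | 0.58, 0.54, 0.50 |
| Lymphocytes (/uL) | 500 | 800, 1,000, 1,200 | 0.62, 0.50, 0.42 |
| Neutrophils (/uL) | 1,500 | 1,500, 1,800, 2,000 | 1.00, 0.83, 0.75 |

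For the first three analytes the floor is below every LLN tried.

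**Step 2: what does the table show if the value then halves?** Haemoglobin goes from 8 to 4, platelets from 75,000 to 37,500, lymphocytes from 500 to 250. Each is L before and L after. The cell is L to L in all 4 + 3 + 3 = 10 combinations. Neutrophils differ: at an LLN of 1,500 a patient at the floor is N, so the fall shows as N to L. At 1,800 and 2,000 it is again L to L.

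**Step 3: patients normal at baseline.** Take an assumed haemoglobin LLN of 12 g/dL. A lowest value of 11.5 and a lowest value of 6.5 are both below 12, so both patients fall in the N to L cell.

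**Step 4: what do the other outputs show?** Suppose one patient's haemoglobin falls by 4 g/dL and the others do not change. The mean moves by 4/n: 4/40 = 0.10 g/dL with 40 patients and 4/10 = 0.40 g/dL with 10. The mean hides the fall, but the minimum change at that visit is -4, so the by-visit summary shows it if it occurs at a scheduled visit. SAP 5.5 keeps unscheduled laboratory values in listings and out of summaries.

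- The minimum gives the deepest value or change at a visit. It does not say how many patients worsened or from what level, and the lowest value and the largest fall may belong to different patients.
- The listing holds every value but counts nothing. A patient low from the start may be flagged throughout.
- The graded adverse event tables include a laboratory fall only if the investigator considers it clinically relevant (Protocol 5.2.5.4).

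By contrast, SAP 5.10.5 plans each patient's minimum and change to minimum for vital signs. SAP 5.10.4 has no equivalent for laboratory values.

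**The case against.** The strongest reply is that a severe fall would not go unseen. The by-visit minimum would show it, the listing would flag it, and values far below normal would probably be reported as adverse events, graded by CTCAE and counted among those of grade 3 or higher. The enrolled group is likely to be small, since SAP 4.1 says the study closed early after slow enrolment, so the listing can be read patient by patient. The SAP also already improves on the protocol by using the highest and lowest values instead of the last one. Nothing in the documents requires a grade shift, and nothing here is contradictory.

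Most of that stands. A reader might infer that patients could worsen badly with nothing in the report to show it. The documents do not support that, because three other outputs can show the fall. A reader might also infer that the shift table is the intended detector of a known signal and would miss it. No section gives the table that role. What the previous studies of this drug showed was a mild fall in total leukocytes, and the low-to-low result above is shown for haemoglobin, platelets and lymphocytes. Nor is this a monitoring gap, since haematology is scheduled at every visit in Protocol Table 1.

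What the reply leaves open is the count. None of these outputs gives the number of patients by severity of laboratory worsening without relying on the investigator's decision to report an event.

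**Conclusion.** The point holds as a limited weakness in safety reporting. The shift tables cannot show worsening below the reference range, and no other planned table counts patients by its severity. Primary efficacy is unaffected, and Protocol 7.1.2 plans no safety hypothesis test.

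The structural result depends on assumed lower limits of normal, but for haemoglobin, platelets and lymphocytes it was the same at every limit tried. The number of patients affected cannot be derived: the documents give no baseline laboratory data. It is tempting to apply a guessed share of low-at-baseline patients to the planned maximum of 40. Both the share and the denominator would be unsupported, given the early closure.

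**What to change.** Keep the low/normal/high tables, which serve the reference-range comparison promised in Protocol 7.1.2. Add to SAP 5.10.4, for haemoglobin, leukocytes, neutrophils, lymphocytes, platelets, ALT, AST, bilirubin and creatinine:
- a shift table of baseline CTCAE v4.03 grade against worst post-baseline grade;
- the number and percentage of patients at grade 3 or higher;
- the number and percentage with a rise of two or more grades.

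State whether unscheduled values count towards the worst grade, because SAP 5.5 would otherwise leave them out.

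The cost is a small amount of programming and one more set of tables. The scale is already the trial's adverse event scale, and the laboratory data are already collected.
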